Postoperative course. Within the recovery room following surgery, the stimulators will be attached to the leads and activated, followed by end point assessment. Subjects who had a spinal anesthetic will have end points recorded following spinal resolution. Operating and recovery room pharmacologic analgesic requirements will be recorded.

Post-hospital course. Prior to discharge, subjects and their caretakers will be provided with verbal and written stimulator/lead instructions and the telephone and pager numbers of a local investigator available at all times. Subjects will be discharged home with their leads *in situ*, and contacted every-other day by a healthcare provider until lead removal. Subjects will be also be discharged with a prescription for immediate-release oral oxycodone (5 mg tablets taken for breakthrough pain).

Therefore, *all* patients of this study—regardless of the treatment arm they are randomized to—will continue to receive current usual and customary analgesia. Subjects will be contacted by telephone for end point collection. Lead removal will occur on postoperative day 14 (+/- 2 days) by healthcare providers. If the lead is removed following Day 14, the stimulator will be turned off on Day 14 and removed subsequently. Similar to perineural catheters,¹³⁵ this procedure encompasses simply removing the occlusive dressing and gently pulling on the lead. Following study completion, the results will be mailed electronically or by the United States Postal Service to all enrolled subjects in written form using non-technical language.

Outcome measurements (end points). We have selected outcome measures that have established reliability and validity, with minimal inter-rater discordance, and are recommended for pain-related clinical trials by the World Health Organization and the Initiative on Methods, Measurement, and Pain Assessment in Clinical Trials (IMMPACT) consensus statement.¹³⁶ Importantly, nearly all outcome measures are common data elements from the National Institute of Neurological Disorders and Stroke (NINDS).¹³⁷ End points (Table 2) will be evaluated at baseline (prior to surgery on postoperative day 0), during the treatment period (postoperative days 1-14); and the follow-up period (postoperative day 15 and months 1, 4, and 12).

Table 2. Summary of post-enrollment assessments (color added for clarity)

Time Point:	Postoperative Days								Postoperative Months		
	0	1	2	3	4	7	11	15	1	4	12

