Opioid consumption previous 24 h	•	•	•	•	•	•	•	•	•	•	•
Average Pain [NRS]	•	•	•	•	•	•	•	•	•	•	•
Worst Pain [NRS]	•	•	•	•	•	•	•	•	•	•	•
Brief Pain Inventory, Short Form	•			•		•		•	•	•	•
Defense and Veterans Pain Rating Scale	•			•		•		•	•	•	•
World Health Organization Quality of Life Instrument	•								•	•	•
Post-Traumatic Stress Disorder Checklist (C)	•										
Masking Assessment		•									

Demographic and medical history. Subjects will have demographic and anthropomorphic data collected based on NINDS case report form General Core and Demographics Modules and Guidelines, including age, sex, height, weight, educational level, employment status, marital status, and U.S. military service (e.g., none, discharged, active). In addition, the medical history based on the common data elements of the NINDS Medical, Family, Behavioral History, History of Disease/Injury Event, and Prior and Concomitant Medications Sub-Domains will be collected, and include the mechanism of original injury, medications (including analgesics), previous surgical procedures, comorbidities, existing sensory deficits of the target nerve distribution, preoperative pain levels measured on a Numeric Rating Scale for pain (including daily least, average, worst and current), and muscle strength if applicable (measured with a pressure transducer; **Table 1**). In addition, since post-traumatic stress disorder (PTSD) may be associated with the severity of pain,¹³⁸ at baseline we will apply the PTSD Checklist (PCL-C), a 20-item self-report measure reflecting symptoms of PTSD validated in military,¹³⁹ Veteran,¹⁴⁰⁻¹⁴² and civilian populations.¹⁴³

Postoperatively, surgical endpoints will be recorded such as surgical duration, tourniquet duration (if applicable), analgesic administration, anesthetic administered, and any sedative agents provided. In addition, subjects will have baseline end points measured including a pain score at the surgical site using the Numeric Rating Scale (NRS, 0-10). **The remaining end points of Table 2 are described in detail under each Hypothesis in the UH3 Implementation Phase section description below.**

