enrolling site, with the case report forms faxed to the Principal Investigator at the University California San Diego using a secure fax machine in a locked office to protect personal health information. All data collection following the day of surgery will occur by telephone from the University of California San Diego, which will then enter all data to the database. For the UG3 feasibility study, the final data collection point for each subject will be at 4 months following surgery (the 12-month time point will be used for the definitive UH3 pragmatic clinical trial). Quality assurance will be ongoing by the University of California San Diego, which will monitor data for sources of error and report to the Medical Monitor (DSMB Chair) with written monthly reports. Each enrolling center will be expected to enroll at least 1 subject for each of the 3 possible lead locations (e.g., brachial plexus trunks) in each of the first two quarters of the 2nd year of the funding period. Combined, the 7 centers will enroll a total of 64 subjects as part of the feasibility study.

Preparation for the UH3 Clinical Trial. If one or more centers fails to enroll their designated subjects—for whatever reason(s)—other centers will make up this enrollment with coordination by the Principal Investigator. The 64-subject feasibility study will enable evaluation of the study intervention, protocol, case report forms, outcome measures, data-entry platform, Research Coordinators, Site Directors, and study oversight. Any changes deemed necessary by the Principal Investigator in concert with the DSMB, funding agency, Steering Committee, Site Directors and NIH-DoD-VA Pain Management Collaboratory Coordinating Center will be made to any aspect of the study design (such as the outcome measures or informed consent forms), including replacing any enrolling center that fails to demonstrate the ability to adequately enroll and execute the protocol. The data from the first 64 subjects will be cleaned by University of California San Diego and a statistical analysis performed by the study statistician ([name]) at the Department of Outcomes Research (Cleveland Clinic).

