The 4-year UH3 Implementation Phase will include a multicenter, randomized, triple-masked, placebo-controlled, parallel-arm, human subjects pragmatic clinical trial. The primary Specific Aim of the trial is to determine the effect of percutaneous PNS on postoperative **opioid** requirements and **analgesia** following moderate-to-severely-painful ambulatory surgery (under the usual conditions in which PNS will be applied, making this a “pragmatic trial”). Secondary Specific Aims are to determine the effect of percutaneous PNS on physical and emotional **functioning, chronic pain, and quality of life** following moderate-to-severely-painful ambulatory surgery. The definitive UH3 pragmatic clinic trial will use the same protocol as the UG3 Planning Phase feasibility study described above, with the addition of any revisions determined necessary following that initial investigation. We will work closely with the NIH-DoD-VA Pain Management Collaboratory Coordinating Center at all phases of the definitive pragmatic clinical trial, from preparation through data analysis and manuscript preparation.

The primary end points will be cumulative opioid consumption and average surgical pain (measured with a Numeric Rating Scale) within the first 7 days following surgery. The primary analyses will compare the two treatment groups, one of which will receive active stimulation while the other will receive no stimulation.

Hypothesis 1 (UH3): Opioid consumption will be significantly decreased within the first 7 days following surgery with percutaneous PNS compared with usual and customary analgesia.

Opioid analgesic consumption [oxycodone 5 mg tablets] will be recorded at all time points (**Table 2**), ***with the primary end point being the cumulative opioid dose for postoperative days 0-7*** (see statistical section for further details).

Hypothesis 2 (UH3): Surgical pain will be decreased within the first 7 days following surgery with percutaneous PNS compared with usual and customary analgesia (measured with a Numeric Rating Scale).

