We will first test for noninferiority of PNS to usual care on each of the two outcomes using 1-tailed noninferiority tests. The noninferiority deltas will be 1 point (worse) in pain score and 20% higher in opioid consumption. Noninferiority will be assessed at the overall 0.05 significance level with no adjustment to the significance criterion for testing two outcomes since noninferiority is required on both outcomes – i.e., an intersection union test. A noninferiority delta of 1 point in pain score is conservative since receiver operating characteristic curve analysis has demonstrated that changes from baseline of at least 1.7 along a 10-point NRS accurately identified patients who rated improvements as “much improved” or more, compared with those who perceived no change or worsening following analgesic interventions.^{153,156,177-179}

We will assess noninferiority on pain score using a one tailed t-test which incorporates the noninferiority delta of 1 point. The estimated treatment effect for pain score will be derived from a linear mixed effects model with the outcome of patient’s “average” pain score for each day, with fixed effects for intervention (PNS vs usual care) and time (days 1 through 7), and assuming an autoregressive correlation structure among and measurements on the same patient overtime. We will then test for noninferiority with a one tailed t-test in which the numerator is the estimated treatment effect from the model minus the noninferiority delta (1), and the denominator is the standard error of the estimated treatment effect. This method will yield results similar to comparing groups on the patient mean of these seven days, but is more flexible since it allows for missing data and also directly accounts for the correlation within patient. The model also allows assessing the treatment by time interaction, but this will most likely not be of interest.^{180,181}

Cumulative opioid consumption is not typically normally distributed, but usually approximates a log-normal distribution. We therefore plan to assess the treatment effect of PNS versus usual care on the log transformed cumulative consumption through POD 7 using a simple linear regression model (equivalent to a t-test). The estimated treatment effect (i.e., difference between groups) will then be used in a noninferiority test with null and alternative hypotheses as: $H_0: \mu_1 - \mu_2 \geq \log(1.2) =$

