Planning Phase sample size considerations. The sample size for the planning phase of 64 patients will be sufficient to estimate the treatment effects of interest with moderate precision, i.e., a confidence interval width of roughly 1.1 standard deviations for each outcome measure. Confidence interval width for a standard deviation estimate will be 0.70 standard deviations. The planning phase will be sufficient to use in estimating the expected treatment effect and standard deviation for each outcome for the larger trial.

UH3 Implementation Phase. Statistical methods for the UH3 Implementation Phase will follow very closely the methods described for the UG3 Planning Phase. The main difference is that UH3 Implementation Phase will have sufficient data to conduct the subgroup analyses and also considerably more power to assess the treatment effects of interest.

Another substantive difference from the planning phase is that in the full trial we will conduct interim analyses at each 25% of the planned enrollment using a group sequential method with gamma spending function and gamma parameter of -4 (quite conservative) for efficacy and 0 (moderately aggressive) for futility (**Figure 14**). The probability of crossing a boundary for either efficacy (mainly) or futility at the first through fourth looks would be 0.10, 0.42, 0.80 and 1.0, respectively, assuming the alternative hypotheses were true.

Figure 14. Stopping boundaries for 1-tailed tests for superiority for either pain score or opioid consumption. Blue region indicates superiority (reduced opioid consumption or pain score) and pink region indicates futility (lack of superiority). Z-statistic represents strength of evidence against the null hypothesis, either ratio of means or difference in means divided by standard error.

Missing outcomes data will be summarized along with the etiology of the absence. | While very little outcomes data is expected to be missing,

analyses will be intention to treat, and imputation of missing data using methods such as multiple imputation and last observation carried forward will therefore be utilized, based on the situation. In a conservative analysis imputation will involve the conservative approach of assigning the worst observed outcome to patients in intervention groups and best observed outcomes to those in control.

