15. RISK MANAGEMENT PROCEDURES AND ADEQUACY OF RESOURCES

The principle protection for participants and the true foundation for conducting a safe and effective clinical study is a well-trained and caring research staff. The principle investigator of this proposal, [name], is an experienced multicenter clinical trial Principal Investigator with a Master's of Science Degree in Clinical Investigation that included multiple classes specifically addressing the ethical conduct of human subjects research. [name] has published special articles within peer-reviewed journals specifically addressing this issue ([name]: Informed consent for medical research: an ethical imperative. *Reg Anesth Pain Med* 2006; 31: 353-7. PMID: 16857555). All study personnel will receive training in human subjects protection and compliance with the HIPAA regulations.

Subjects will be given clear instructions to call an investigator with any questions or concerns regarding their study participation. If a patient experiences an injury that is directly caused by this study, only professional medical care that they receive at the medical center. No other compensation is offered. Any adverse events will be reported to the IRB using the standard adverse events reporting and upon continuing review (depending on severity, as defined by the IRB). During stimulation, subjects will be contacted daily by an investigator, and subjects will have a physicians' pager and cellular phone numbers available to respond 24 hours/day and 7 days/week until the day following lead removal. This procedure has proven effective for ambulatory surgical patients with perineural local anesthetic infusions (continuous peripheral nerve blocks).

Precautions and responses to possible specific adverse events:

Infection: Leads will be placed under sterile conditions as is standard-of-care for any percutaneous device insertion. In addition, all patients having orthopedic surgical procedures receive perioperative antibiotics, which will further decrease any risk of infection. Subjects will be called daily and asked

about signs and symptoms of lead infection. Should a lead become infected, it will be removed and oral antibiotics prescribed.

Lead fracture: It remains unknown what leads to lead fracture in a small percentage of patients, and therefore we cannot take specific steps to minimize its occurrence other than removing the leads with continuous, gentle traction.

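### The days 0-7 opioid total has no recorded dose for days 5 and 6 in any patient, and the plan gives no rule for filling the gap

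*Combined protocol and SAP*

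**What the plan says.** Section 9, Hypothesis 1 (UH3), names the data source and the endpoint together: "Opioid analgesic consumption [oxycodone 5 mg tablets] will be recorded at all time points" of Table 2, "with the primary end point being the cumulative opioid dose for postoperative days 0-7". It refers to the statistical section for details.

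The opioid row of Table 2 is labelled "Opioid consumption previous 24 h". The columns are days 0, 1, 2, 3, 4, 7, 11 and 15 and months 1, 4 and 12. There is no day-5 or day-6 column.

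The statistical section analyses "log transformed cumulative consumption through POD 7 using a simple linear regression model". It does not say how the total is put together from the records. Its missing-data paragraph expects very little missing outcome data and says that "multiple imputation and last observation carried forward will therefore be utilized, based on the situation".

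The Enrollment paragraph of the UG3 milestones makes the central calls the only source after day 0: "All data collection following the day of surgery will occur by telephone from the University of California San Diego". Two other contacts are mentioned. Under Post-hospital course, subjects are "contacted every-other day by a healthcare provider until lead removal". Section 15 says: "During stimulation, subjects will be contacted daily by an investigator". Neither contact is said to record opioid use, and no diary or tablet count is described.

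**The concern.** A cumulative dose needs every day in the period. Here two days are missing by design, for everyone, so this is not the sporadic loss that the missing-data paragraph has in mind. Multiple imputation has no observed value in those windows to learn from. Anything it produced would come from an assumed shape between day 4 and day 7. Carry-forward is one option among several, and the plan does not commit to it.

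Two analysts who both follow the plan could therefore report different opioid effects from the same patients. The dose on those days cannot be recovered as scheduled 24-hour records once the calls have been made. The pilot uses the same schedule and supplies the sample-size inputs for the main trial, so the gap reaches the sizing step as well.

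A varying effect is plausible, though this is an inference. Both arms receive a single-injection nerve block, and surgeons may add local infiltration, which could mask an early difference.

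**Working it through.** **Coverage.** A 24-hour look-back on days 1, 2, 3, 4 and 7 covers the windows 0-1, 1-2, 2-3, 3-4 and 6-7. Windows 4-5 and 5-6 are never asked about: 2 of 7, or 28.6% of the period. Reading days 0-7 as eight calendar days still leaves days 5 and 6 without a record. The share of the control dose in the gap depends on the use pattern (assumed): 29% if use is flat, 19% if it falls 20% per day, 9% if it falls 40% per day.

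**The plan's own sample size.** Inputs from the UH3 sample-size paragraphs: 20% reduction, CV 0.75, one-sided 0.0125, 90% power. In natural logs, SD = sqrt(ln(1 + 0.75²)) = 0.668.

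- Per arm: 2 × (2.241 + 1.282)² × 0.668² / (ln 0.8)² gives 223, so 446 in total. The t-based version gives 448, as stated.
- Four looks with the stated spending functions and non-binding futility inflate this by 1.177, to about 527 against the stated 528.

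The stated numbers stand and are not affected by this point.

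**Effect of the filling rule.** SE = 2 × 0.668 / sqrt(448) = 0.0631. Power = Phi(|ln ratio| / 0.0631 − 2.241). Each assumed profile is scaled so that the true seven-day ratio is 0.80, which has 90% power with complete data. Carry-forward (CF) sets days 5 and 6 to the day-4 value. Interpolation (INT) draws a straight line, so days 5 + 6 = day 4 + day 7.

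| Effect pattern | Flat use: CF / INT | Falling 20%/day: CF / INT | Falling 40%/day: CF / INT |
|---|---|---|---|
| Constant | .800 / .800 | .800 / .800 | .800 / .800 |
| From day 3 | .800 / .800 | .789 / .798 | .767 / .791 |
| Rising from 0 | .829 / .800 | .818 / .806 | .794 / .803 |
| Fading to 0 | .771 / .800 | .790 / .797 | .802 / .799 |

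Across these 12 profiles, power runs from 98% to 77% with carry-forward and from 93% to 88% with interpolation.

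**Less smooth patterns, flat use of 1 unit per day.** A true ratio of 0.80 removes 1.4 of 7 units.

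- Effect starting on day 5: each of days 5-7 is 1 − 1.4/3 = 0.533. CF: (4 + 2 + 0.533)/7 = 0.933, power 13%. INT: (4 + 1.533 + 0.533)/7 = 0.867, power 51%.
- Effect on days 1-4 only: each is 1 − 1.4/4 = 0.65. CF: (2.6 + 1.3 + 1)/7 = 0.70. INT: (2.6 + 1.65 + 1)/7 = 0.75. Both overstate the benefit.

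**Extra variance carried into the pilot SD.** In simulated lognormal patients with no zero use, the SD of the log total rose by 0-3% with interpolation and 0-7% with carry-forward. A second set of assumptions allowed zero use (Poisson tablets, 1-3 per day at first, patient log SD 0.6, log(x + 1)). The SD ratios were then 1.04-1.12 and 1.08-1.16. Sample size scales with the square, so the upper ends are 1.12² = 1.25 and 1.16² = 1.35. The size of this effect therefore rests on the assumptions.

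**The case against.** The case for leaving the plan alone has real substance.

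- A total can still be derived, and with a constant daily effect both rules give exactly 0.80 and 90% power. This stands, but the plan gives no reason to assume a constant effect.
- The missing-data paragraph could be stretched to cover the gap. It names methods but does not choose one, and it does not address windows that are unscheduled for everyone.
- UH3 statisticians are masked until the analysis is complete, which limits a result-driven choice of rule. It does not make the estimate independent of the rule.
- The overall claim needs superiority on one outcome and at least noninferiority on the other, so a pain benefit could carry it. At the worst ratio shown, 0.933, the opioid estimate lies (0.182 + 0.069)/0.0631 = 4.0 standard errors from the 1.2 margin. This stands as a limit on the harm.
- The pilot is meant to test forms and outcome measures, and the UH3 plan may then be revised. That can repair the main trial but cannot recover the pilot's own windows.
- The powers above are for a fixed design with one endpoint, not the planned 528 with four looks and joint testing. They show direction and rough size only.

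A reader might go further and infer that the trial risks a false positive. The documents do not support that: with no effect on any day, a rule fixed in advance creates none. A reader might also expect the analysis to sum only the five recorded windows, which would distort the result more. The plan names no such sum, and a total lacking two days is not the stated endpoint.

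**Conclusion.** The point holds: as written, the plan does not collect all of its opioid primary endpoint. Two of seven postoperative windows are unrecorded in every patient, and no rule or other source covers them. It should be fixed before the pilot starts.

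The count follows from Table 2 alone. The size of the consequence rests on assumed use and effect profiles. There is no bias in the ratio under a constant effect, a modest shift under smooth variation, and a large loss of power if the effect appears mainly after day 4.

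Two readings should be avoided, in opposite directions. One is that the endpoint is unusable or the sample size wrong: a total can be derived, and 448 and 528 reproduce. The other is that interpolation makes the bias small, or that the variance penalty has a known ceiling. The day-5 and zero-use examples show that neither is a bound.

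The pain endpoint shares the day-5 and day-6 gap, but its effect remains estimable from days 1, 2, 3, 4 and 7 with the planned mixed model.

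**What to change.** Starting in the pilot, use the existing day-7 call to record all oxycodone tablets taken since the day-4 call, and define the primary total from that count. Keep the 24-hour question at the same call. Prespecify one fallback, for example straight-line interpolation between days 4 and 7, only for patients in whom the count is not obtained, with a sensitivity analysis under another rule.

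The cost is one question on a scheduled call, form wording and a short derivation text in the statistical section. The downside is recall over two to three days, which is less exact than 24-hour recall.

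Separate minor points to reconcile in the same revision:

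- Hypothesis 4 names 6 and 12 months, but follow-up is at months 1, 4 and 12.
- The pain window is days 0-7 under Hypothesis 2 and days 1-7 in the statistical model.
- Day 0 covers both a preoperative baseline and recovery-room recording; state which day-0 records enter each primary endpoint.
- The two descriptions of contact frequency during stimulation (Post-hospital course and section 15) differ.

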Current/present, worst, least, and average pain at the surgical site will be assessed using a Numeric Rating Scale (NRS) as part of the Brief Pain Inventory (short form). The Brief Pain Inventory is an approved NINDS common data elements Scale. The use of single items (e.g., average pain) in addition to the composite score is supported by the IMMPACT recommendations for assessing pain in clinical trials. The NRS will be recorded at all time points (**Table 2**), ***with the primary end point being the mean value of the “average” pain scores for postoperative days 0-7*** (see statistical section for further details). The NRS is a highly-sensitive measure of pain intensity with numbers

ranging from 0 to 10, zero equivalent to no pain and 10 equivalent to the worst imaginable pain. The NRS has been demonstrated to be a valid and reliable measure following analgesic interventions. In addition, NRS scores correlate well with other measures of pain intensity, and demonstrate high test-retest reliability. These NRS characteristics led to recent IMMPACT consensus recommendations for use of the 10-point NRS of pain intensity for pain trials.

An additional instrument, the Defense and Veterans Pain Rating Scale (DVPRS), will be utilized at various time points following surgery. The DVPRS was developed specifically for—and subsequently validated in—active duty military and Veteran patient populations. Unfortunately, this new instrument has not been validated for repeated measures, and therefore will not be used as a primary end point for the current investigation. However, future pain-related investigations involving military personnel and Veterans will undoubtedly use the DVPRS, and we want the results of the current study to be comparable. Therefore, we will use the DVPRS as a secondary end point at various time points (not all to lessen the questionnaire burden on subjects).

Primary end point: *In order to claim that percutaneous PNS is superior to usual and customary analgesia, at least one of Hypotheses 1 and 2 above must be superior while the other either superior or at least noninferior.*

Hypothesis 3 (UH3): Physical and emotional **functioning** will be significantly improved in the 12 months following ambulatory surgery with percutaneous PNS as compared with usual and customary analgesia (measured with the Brief Pain Inventory).

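### The primary-endpoint window is inconsistent: both endpoints are defined over days 0-7, day 0 is labelled the pre-surgery baseline, pain is modelled over days 1-7, and opioid has no start point

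*Combined protocol and SAP*

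**What the plan says.** All references are to Section 9 unless stated.

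- **Hypothesis 1 (UH3):** opioid is recorded at the Table 2 time points, "with the primary end point being the cumulative opioid dose for postoperative days 0-7".
- **Hypothesis 2 (UH3):** the pain endpoint is the mean of the daily average "pain scores for postoperative days 0-7". Both hypotheses send the reader to the statistical section for detail.
- **Outcome measurements and Table 2:** end points are "evaluated at baseline (prior to surgery on postoperative day 0", and the treatment period is given as days 1-14. Table 2 has one day 0 column and no separate baseline column. That column also holds the PTSD checklist, which the text says is applied at baseline. Opioid is recalled over the previous 24 hours.
- **Treatment group assignment and Postoperative course:** allocation happens only once surgery has begun. The stimulator is activated in the recovery room and end points are then assessed. Figure 11 starts the treatment schedule on day 0.
- **Statistical Plan, pain:** a mixed model "with fixed effects for intervention (PNS vs usual care) and time (days 1 through 7"), described as similar to "comparing groups on the patient mean of these seven days".
- **Statistical Plan, opioid:** a regression on "log transformed cumulative consumption through POD 7", with no first day named.
- **Statistical Plan, margins:** 1 point for pain and 20% for opioid. Noninferiority is required on both outcomes. The definitive trial follows the pilot's methods very closely.

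**The concern.** A value taken before surgery precedes randomisation, so treatment cannot change it. If it enters the outcome, the between-group difference in mean pain shrinks. For a superiority test this is conservative. For a noninferiority test it is not, because real harm on the treated days is also shrunk and passes more easily. Both outcomes must pass noninferiority before any claim of superiority, so the window matters on both.

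Even if no pre-surgery value is ever used, two written windows for the same primary endpoint permit two primary results. The 64-subject pilot also supplies the effect and variance estimates for the definitive sample size, so an unsettled window carries into that calculation.

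**Working it through.** **1. Windows side by side**

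| Source | Pain | Opioid |
|---|---|---|
| Hypotheses 1 and 2 | days 0-7 | days 0-7 |
| Outcome measurements, Table 2 | day 0 = pre-surgery baseline | day 0 = previous 24 h |
| Postoperative course, Figure 11 | day 0 also has a post-activation assessment | day 0 also has recovery-room analgesic use |
| Statistical Plan | days 1-7, seven days | up to day 7, no start |

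The pain windows contradict each other. For opioid, the statistical section does not settle the start. Nothing says which day 0 value counts, if any.

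**2. The plan's own sample size.** Inputs from the UH3 sample size paragraph: 20% reduction, CV 0.75, one-sided alpha 0.0125, power 90%, 1:1 allocation.
- Log-scale SD = √ln(1 + 0.75²) = 0.668; effect = ln 0.8 = −0.223.
- n per arm = 2 × (0.668/0.223)² × (2.241 + 1.282)² ≈ 223, so 446 in total; the t-based version gives 448, as stated.
- Four looks with the stated spending functions (non-binding futility) give inflation 1.177, and 448 × 1.177 ≈ 527 against 528 stated.

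The stated figures reproduce.

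**3. Pain, if a pre-surgery score were averaged in.** Assume a constant effect on treated days and none on day 0. Table 2 schedules days 0, 1, 2, 3, 4 and 7 (six scores, five treated); a full daily series has eight (seven treated).
- Observed effect for a true 1 point: 5/6 = 0.833, or 7/8 = 0.875.
- Harm on treated days that just meets the 1-point margin: 1/0.833 = 1.20, or 1/0.875 = 1.14.
- Power at N = 528 (264 per arm), SD held at 2, fixed-design formula: SE = 2 × √(2/264) = 0.174. Power = Φ(effect/SE − 2.241) = 0.9998 for 1.0, 0.997 for 0.875 and 0.995 for 0.833.

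**4. Pain, as modelled (days 1-7).** The effect stays at 1.0 and the margin at 1.0.

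**5. Opioid, if a pre-surgery dose were counted.** Let f be that dose as a fraction of the control arm's later total, equal in both arms. The documents give no f, so a range is assumed. The observed ratio is (0.8 + f)/(1 + f), and the true ratio that just meets the 1.2 margin is 1.2 + 0.2f.

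| f (assumed) | Observed ratio | Effective margin | Power at N = 448, fixed design |
|---|---|---|---|
| 0 | 0.800 | 1.200 | 0.90 |
| 0.05 | 0.810 | 1.210 | 0.87-0.89 |
| 1/7 | 0.825 | 1.229 | 0.79-0.88 |

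The lower power holds the CV at 0.75; the upper lets it fall to 0.75/(1 + f), as it would if a constant dose were added. The absolute difference in dose does not change.

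**The case against.** A reader might infer that the trial does average an untreated score and dose into its outcomes, and so weakens the effect and widens the noninferiority margin. The documents do not support that.

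- The endpoint text defers to the statistical section, whose pain model leaves day 0 out.
- Day 0 is not only a baseline. It is the day of surgery, with stimulation started and end points assessed in the recovery room. Including day 0 can reasonably mean including postoperative data from that day.
- Both primary endpoints are introduced as covering the first week after surgery, and the opioid named is the tablet prescribed at discharge. Nowhere is preoperative intake said to be added.
- Opioid is a sum, not an average. Section 10 excludes chronic analgesic users, so preoperative intake should be near zero for most subjects.
- The margins are fixed numbers. Only an effective margin moves, and only under one reading.
- Pain power is barely touched under any reading.

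All of this stands, and it makes the figures in step 3 conditional. It does not remove the contradiction between the two pain windows or supply an opioid start point. The recovery-room assessment adds to the ambiguity, because there are then two candidate day 0 values, the second taken after the single-injection block that every subject receives.

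It can also be said that leaving out a baseline covariate is not an error, since the plan already considers adjusting for variables with a standardised difference above 0.10. That is fair. Still, adjustment triggered by observed imbalance is weaker than a covariate named in advance, and the score is already collected.

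**Conclusion.** The inconsistency is real and sits in the definition of both primary endpoints, so it should be resolved before any analysis. Its numerical effect depends on how it is resolved:

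- **Pain, days 1-7 as modelled:** no dilution and no change in the margin.
- **Pain, days 0-7 with the pre-surgery score:** a 1-point effect becomes 0.83-0.875, and up to 1.14-1.20 points of harm on treated days meets the margin. Power stays at about 0.995 or higher. This assumes a constant effect on treated days and an SD of 2.
- **Opioid:** any counted pre-surgery dose pulls the ratio towards 1. At an assumed 5% of the control total, it moves from 0.80 to 0.81. Larger fractions are possible arithmetically but unlikely given the exclusion criteria.

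The case rests on an ambiguous primary endpoint and on the noninferiority requirement, not on lost power for pain.

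**What to change.** State one window per endpoint, in the same words under Hypotheses 1 and 2 and in the Statistical Plan.

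- **Pain:** days 1-7, as already modelled. Enter the pre-surgery day 0 score as a prespecified baseline covariate in the primary mixed model, whatever the observed imbalance.
- **Opioid:** consumption after surgery and stimulator activation through day 7. State that the pre-surgery 24-hour recall is excluded.
- **Table 2:** split day 0 into a pre-surgery column and a post-activation column, so that each value has one use.

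The cost is a wording change and one covariate. No new pain data are needed. Day-of-surgery opioid use must be recorded separately from pre-surgery intake. The stated sample size does not change on this account.
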